17.3 Primary endpoint

The primary endpoint is the change from baseline in HbA_{1c} 16 weeks after randomisation.

Primary analysis

1) The primary estimand will be addressed by the below primary analysis based on all Subjects included in the FAS and using the in-trial observation period. Note that if Subjects withdraw consent to contribute additional information or are completely lost to follow-up, missing data will still occur. The primary analysis will be implemented as a statistical model using multiple imputations where the Subjects without any available HbA_{1c} measurements at scheduled visits will have their HbA_{1c} value imputed from the available information from the treatment the Subject has been randomised to. Note that this resembles in essence a mixed model of repeated measurements analysis, but Subjects without post-randomisation measurements contribute to the analysis, as the missing values will be imputed. The analysis will be implemented as follows:

Protocol		Date:	04 February 2016	Novo Nordisk
Trial ID: NN1218-3854	CONTENDENTAL	Version:	4.0	

UTN: U1111-1118-2480

EudraCT no.: 2010-024054-11

• In the first step, intermittent missing values are imputed using a Markov Chain Monte Carlo (MCMC) method, in order to obtain a monotone missing data pattern. This imputation is done for each group separately and 100 copies of the dataset will be generated.

Status:

Page:

Final

111 of 149

- In the second step, for each of the 100 copies of the dataset, an analysis of variance model with strata (two levels based on use of own CGM or not), previous insulin use (three levels: NovoRapid[®], Apidra[®] (insulin glulisin), Humalog[®] (insulin lispro) and region as factors, and baseline HbA_{1c} as a covariate is fitted to the change in HbA_{1c} from baseline to week 4 for each treatment group separately. The estimated parameters, and their variances, from these models are used to impute missing values at week 4 for Subjects in each treatment group, based on strata, previous insulin use, region and baseline HbA_{1c}
- In the third step, for each of the 100 copies of the dataset, missing values at week 8 are imputed in the same way as for week 4. The imputations are based on an analysis of variance model with strata, previous insulin use and region as a factors and baseline HbA_{1c} and change from baseline in HbA_{1c} at week 4 as covariates.
- This stepwise procedure is then repeated sequentially for week 12 and 16
- For each of the complete data sets, the change from baseline to week 16 is analysed using an analysis of variance model with treatment, strata, previous insulin use and region as factors, and baseline HbA_{1c} as a covariate.
- The estimates and standard deviations for the 100 data sets are pooled using Rubin's formula:

$$m_{MI} = rac{1}{100} \sum_{i=1}^{100} m_{i,}$$
 ,

$$SD_{MI} = \sqrt{\frac{1}{100} \sum_{i=1}^{100} SD_i^2 + \left(1 + \frac{1}{100}\right) \left(\frac{1}{100 - 1}\right) \sum_{i=1}^{100} (m_i - m_{MI})^2}$$

where m_i and SD_i are the estimated means and standard deviations for the 100 copies of the dataset, and m_{MI} and SD_{MI} are the pooled estimates.

Protocol		Date:	04 February 2016	Novo Nordisk
Trial ID: NN1218-3854	CONFIDENTIAL	Version:	4.0	
UTN: U1111-1118-2480	CONFIDENTIAL	Status:	Final	

• From m_{MI} and SD_{MI}, the 95% confidence interval for the treatment differences is calculated

Page:

112 of 149

Non-inferiority of faster-acting insulin aspart will be considered confirmed if the upper boundary of the two-sided 95% CI is below or equal to 0.4% or equivalent if the p-value for the one-sided test of

 H_0 : D > 0.4% against H_A : D < 0.4%,

EudraCT no.: 2010-024054-11

is less than or equal to 2.5%, where D is the mean treatment difference (faster-acting insulin aspart minus NovoRapid[®]).

Note that as the anticipated number of Subjects discontinuing treatment, but not trial is low, imputations based on such Subjects will not be suitable.

Provided that the hierarchical testing allows, the evaluation of superiority will be based on the same statistical model, as the primary analysis 1). The associated sensitivity analysis that follows will investigate the robustness of non-inferiority and superiority (analysis 3b and 3c) as well.

Sensitivity analyses for the primary analysis addressing the primary estimand

All sensitivity analyses for the primary analysis addressing the primary estimand will use the in-trial observation period.

- 2) First the primary analysis in 1) will be repeated, but excluding all factors except from treatment in the model. This analysis will explore the influence of the different factors.
- 3) The primary analysis approach chosen for this trial relies on the assumption that missing data is missing at random (MAR). This assumption implies that the HbA_{1c} for Subjects leaving the trial, after their withdrawal, develops in a similar way as the HbA_{1c} for similar Subjects that remain in the trial (not necessarily on treatment) and had similar development of HbA_{1c} before withdrawal. The MAR assumption may be questionable for Subjects withdrawing at own will. Therefore the statistical models using multiple imputation will be repeated with the following alterations:
 - a) Imputations will be done from the treatment arm that the Subject was randomised to and a value of 0.4% (non-inferiority margin) is added to the change from baseline in HbA_{1c} at week16 for Subjects randomised to faster-acting insulin aspart who withdrew from the trial³⁵.
 - b) Imputations will be done from the comparator arm (NovoRapid[®]). This will serve as a sensitivity analysis for the superiority analysis. It does not rely on the MAR assumption, but assumes that all Subjects who withdraw from the trial in the faster-

 Trial ID: NN1218-3854
 CONFIDENTIAL
 Version:
 4.0

 UTN: U1111-1118-2480
 Status:
 Final

 EudraCT no.: 2010-024054-11
 Page:
 113 of 149

acting insulin aspart arm shift to NovoRapid[®]. The imputation will be done such that the treatment effect diminishes gradually after trial discontinuation (copy reference).

c) Imputation will be done from the comparator arm (NovoRapid[®]). This will serve as a supplementary sensitivity analysis for the superiority analysis. It does not rely on the MAR assumption, but assumes that all Subjects that withdraw the trial in the fasteracting insulin aspart arms responded as if they had been on NovoRapid[®] for the entire trial. The imputation will be done such that the treatment effect diminishes immediately after trial discontinuation (jump to reference).

Analyses addressing the secondary estimand

All analyses addressing the secondary estimand will use the on-treatment observation period.

- 4) The secondary estimand will be analysed using the same statistical model using multiple imputations as the primary analysis in 1) except using the on-treatment observation period.
- 5) A tipping point analysis based on a statistical model using multiple imputation model similar to 1), using the on-treatment observation period, will be made. In this analysis observations for Subjects that discontinue randomised treatment are imputed based on the treatment arm they were randomised to and Subjects discontinuing treatment in the fasteracting insulin aspart group are given a penalty. This is done to investigate the robustness of the conclusion in the primary analysis with respect to the MAR assumption and mimics a scenario where the HbA_{1c} of the Subjects discontinuing treatment in the faster-acting insulin aspart groups evolve less favourably than predicted. As a first step imputations will be done without penalty assuming MAR in the treatment group. Second, the imputed values for week 16 in the faster-acting insulin aspart group will be added a penalty. This is done repeatedly, gradually increasing the penalty until the conclusion from the non-inferiority analysis no longer holds. This will serve as a sensitivity analysis for the non-inferiority analysis and the specific value of the penalty that changes the conclusion will be used to evaluate the robustness of the conclusion of the non-inferiority analysis.
- 6) A tipping point analysis based on a statistical model using multiple imputation, similar to 5) but with the modification that Subjects discontinuing treatment due to non-eligibility (Subjects discontinuing faster-acting insulin aspart/NovoRapid® prematurely due to criteria 1, 2, 3, and 4) in the faster-acting insulin aspart group will not have a penalty added. These analyses are motivated by the fact that data from Subjects prematurely discontinuing faster-acting insulin aspart/NovoRapid® due to non-eligibility can reasonably be assumed to be missing completely at random.
- 7) The same statistical model using multiple imputations as the analysis in 4), but using the PP analysis set and analysed using the on-treatment observation period. This analysis will

Protocol	Date:	04 February 2016	Novo Nordisk

 Trial ID: NN1218-3854
 CONFIDENTIAL
 Version: 4.0

 UTN: U1111-1118-2480
 Status: Final

 EudraCT no.: 2010-024054-11
 Page: 114 of 149

investigate the situation that Subjects might have deviated from the inclusion and exclusion criteria and will serve as sensitivity analysis for the non-inferiority analysis.

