- 3) The primary analysis approach chosen for this trial relies on the assumption that missing data is missing at random (MAR). This assumption implies that the HbA_{1c} for Subjects leaving the trial, after their withdrawal, develops in a similar way as the HbA_{1c} for similar Subjects that remain in the trial (not necessarily on treatment) and had similar development of HbA_{1c} before withdrawal. The MAR assumption may be questionable for Subjects

withdrawing at own will. Therefore the statistical models using multiple imputation will be repeated with the following alterations:

- a) Imputations will be done from the treatment arm that the Subject was randomised to and a value of 0.4% (non-inferiority margin) is added to the change from baseline in HbA_{1c} at week 16 for Subjects randomised to fast-acting insulin aspart with an imputed value at week 16.²
- b) Missing values at week 16 will be imputed from the comparator arm (NovoRapid[®]). This will serve as a sensitivity analysis for the superiority analysis. It does not rely on the MAR assumption, but assumes that Subjects on fast-acting insulin aspart with an imputed value at week 16 switch to NovoRapid[®]. The imputation will be done such that the treatment effect diminishes gradually (conditional imputation).
- c) Missing values at week 16 will be imputed from the comparator arm (NovoRapid[®]). This will serve as a supplementary sensitivity analysis for the superiority analysis. It does not rely on the MAR assumption, but assumes that Subjects on fast-acting insulin aspart with missing value at week 16 switch to NovoRapid[®]. The imputation will be done such that the treatment effect diminishes immediately (unconditional imputation).

Analyses addressing the secondary estimand

All analyses addressing the secondary estimand will use the on-treatment observation period.

- 4) The secondary estimand will be analysed using the same statistical model using multiple imputations as the primary analysis in 1) except using the on-treatment observation period.

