- 5) A tipping point analysis based on a statistical model using multiple imputation model similar to 1), using the on-treatment observation period, will be made. In this analysis observations for Subjects without a measurement are imputed based on the treatment arm they were randomised to and Subjects without a measurement in the fast-acting insulin aspart group are given a penalty. This is done to investigate the robustness of the conclusion in the primary analysis with respect to the MAR assumption and mimics a scenario where the HbA_{1c} of the Subjects without a measurement in the fast-acting insulin aspart group evolve less favourably than predicted. As a first step imputations will be done without penalty assuming MAR in the treatment group. Second, a penalty will be added to the imputed values for week 16 in the fast-acting insulin aspart group. This is done repeatedly, gradually increasing the penalty until the conclusion from the non-inferiority analysis no longer holds. This will serve as a sensitivity analysis for the non-inferiority analysis and the specific value of the penalty that changes the conclusion will be used to evaluate the robustness of the conclusion of the non-inferiority analysis.

- 6) A tipping point analysis based on a statistical model using multiple imputation, similar to 5) but with the modification that Subjects without a measurement that discontinued treatment due to non-eligibility (Subjects discontinuing fast-acting insulin aspart/NovoRapid[®] prematurely due to criteria 1, 2, 3, and 4) in the fast-acting insulin aspart group will not have a penalty added to the imputed values. These analyses are motivated by the fact that data from Subjects prematurely discontinuing fast-acting insulin aspart/NovoRapid[®] due to non-eligibility can reasonably be assumed to be missing completely at random.
- 7) The same statistical model using multiple imputations as the analysis in 4), but using the PP analysis set and analysed using the on-treatment observation period. This analysis will investigate the situation that Subjects might have deviated from the inclusion and exclusion criteria and will serve as sensitivity analysis for the non-inferiority analysis.

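### The tipping-point analyses are presented as testing the primary analysis but run on on-treatment data, so their value describes analysis 4 and the in-trial primary result has no tipping search

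*Protocol*

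**What the plan says.** Protocol 17.3 and SAP 2.3 set out two blocks of analyses for HbA1c.

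- **Primary estimand.** Analysis 1 is "based on all Subjects included in the FAS and using the in-trial observation period". On its missing data the plan says: "The primary analysis approach chosen for this trial relies on the assumption that missing data is missing at random (MAR"). A general rule follows: "All sensitivity analyses for the primary analysis addressing the primary estimand will use the in-trial observation period". The analyses under that rule are 2 and 3a to 3c. In 3a, "a value of 0.4% (non-inferiority margin) is added to the change from baseline in HbA_{1c} at week 16" for faster aspart subjects whose week-16 value is imputed (SAP wording). Analyses 3b and 3c impute from the NovoRapid arm and are described as serving the superiority analysis.
- **Secondary estimand.** The block opens with: "All analyses addressing the secondary estimand will use the on-treatment observation period". It contains analyses 4 to 7. Analysis 5 repeats the data period: "A tipping point analysis based on a statistical model using multiple imputation model similar to 1), using the on-treatment observation period, will be made". Analysis 6 inherits it: "A tipping point analysis based on a statistical model using multiple imputation, similar to 5").

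Within the second block, the stated aim of analysis 5 is: "This is done to investigate the robustness of the conclusion in the primary analysis with respect to the MAR assumption". The penalty that changes the conclusion is then to be used to judge how robust non-inferiority is. The SAP changes who is imputed and penalised in analyses 5 and 6 (from subjects who stop treatment to subjects without a measurement). It keeps both the on-treatment period and the stated aim. SAP section 3 does not mention the mismatch.

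**The concern.** A tipping-point value tells a reader how far the missing values would have to depart from the model before a particular conclusion fails. It is informative only about the dataset and imputation from which it was computed.

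The MAR assumption of analysis 1 concerns subjects with no week-16 HbA1c in the in-trial period, chiefly those who withdraw from the trial or are lost. In the on-treatment dataset, HbA1c values taken more than 7 days after the last dose do not count. Subjects who stop product but stay in the trial can therefore be imputed and penalised there, although analysis 1 observes and uses their later values. SAP section 2 also treats Visit 22A and 22B values differently for the two estimands when two values fall on the same visit.

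As written, the report would give a penalty obtained from the data of analysis 4 and offer it as evidence about analysis 1. Protocol 19.2 relies on agreement between the sensitivity analyses and the primary analysis for assurance about the trial's conclusions, so it matters that each is attached to the right result.

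**Working it through.** **1. Data period against stated target**

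| Analysis | Data period | Stated target | Departure from MAR |
|---|---|---|---|
| 1 | in-trial | primary estimand | none (MAR) |
| 3a | in-trial | primary analysis | one fixed penalty, 0.4 |
| 3b, 3c | in-trial | superiority | imputation from NovoRapid arm |
| 4 | on-treatment | secondary estimand | none (MAR) |
| 5, 6 | on-treatment | primary analysis (stated for 5; 6 follows 5) | escalating penalty |

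Only the last row has a target that does not match its data. No row combines in-trial data with an escalating penalty.

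**2. Inputs** (Protocol 17.1, SAP 2.1)

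- Assumed difference -0.1, SD 0.8, 225 per arm, margin 0.4, one-sided 2.5%.
- Treatment discontinuation as low as 4%, half of it trial discontinuation, so 2%.

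**3. The plan's own figure**

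The standard error is 0.8 × √(2/225) = 0.0754. The distance to the margin is 0.4 - (-0.1) = 0.5. A two-group t-test then has power 99.9998%, which agrees with the stated >99.9%.

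**4. Tipping penalty**

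Let d be the starting difference, f the share of the faster aspart arm that is imputed and penalised, and δ the penalty. With t = 1.965 (448 degrees of freedom), solve for δ:

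d + fδ + t × √[(0.8² + 0.8² + f(1 - f)δ²)/225] = 0.4

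The term f(1 - f)δ² is the extra spread in the faster aspart arm from shifting only some subjects. Leaving it out (standard error fixed) gives a simpler upper figure. For d = -0.1 and f = 0.02 that is (0.4 + 0.1 - 1.965 × 0.0754)/0.02 = 17.59. Between-imputation variance is ignored, and f is taken as equal in both arms.

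| d | f | δ, SE fixed | δ, SE inflated |
|---|---|---|---|
| -0.1 | 0.02 | 17.59 | 11.85 |
| -0.1 | 0.04 | 8.79 | 6.78 |
| -0.1 | 0.10 | 3.52 | 3.08 |
| 0 | 0.02 | 12.59 | 8.94 |
| 0 | 0.04 | 6.29 | 5.07 |
| +0.1 | 0.02 | 7.59 | 5.85 |
| +0.1 | 0.04 | 3.79 | 3.25 |

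The 10% share is an assumption, included to show the trend.

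Check of the 11.85: -0.1 + 0.02 × 11.85 + 1.965 × √[(1.28 + 0.0196 × 11.85²)/225] = -0.1 + 0.237 + 0.263 = 0.400.

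**5. What 3a already shows**

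With d = -0.1, f = 0.02 and δ = 0.4, the upper limit is -0.1 + 0.008 + 0.148 = 0.056, far below 0.4.

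**6. Direction**

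At d = -0.1 the in-trial value is 11.85/6.78 ≈ 1.7 times the on-treatment one (2.0 times with the standard error fixed). The on-treatment value is therefore smaller when both datasets start from the same difference. Among the tabulated cases the order still holds if the in-trial estimate is 0 and the on-treatment estimate is -0.1 (8.94 against 6.78). It reverses if they are +0.1 and -0.1 (5.85 against 6.78), a wide gap for two datasets that share most of their values.

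**The case against.** The strongest reply is that this is mostly a labelling error with little effect, and much of that stands.

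- **The imputed subjects overlap.** A subject with no in-trial week-16 value also has none on treatment. The on-treatment imputed set therefore largely contains the primary's missing subjects, plus others. A reader might infer that analysis 5 penalises quite different subjects from those on whom the primary's MAR assumption rests; the documents do not support that.
- **The mismatch errs on the cautious side.** With equal starting estimates the on-treatment search tips earlier, so it would understate the primary's robustness. It would not flatter the result.
- **On-treatment data have a stated reason.** Both documents say the secondary estimand may be the more sensitive for non-inferiority, because switching to marketed product can equalise the arms. That justifies keeping analyses 5 and 6. It does not justify describing them as tests of the primary analysis.
- **The shares are rough.** Visit 22A and 22B values are reallocated to the next scheduled visit (SAP section 2), and a Visit 22A more than 12 weeks after randomisation replaces Visit 22 (Protocol 8.1.8.1). Late discontinuers may thus have a week-16 value in both datasets, so 4% and 2% only approximate the imputed shares.
- **Superiority is covered in-trial.** A reader might infer that HbA1c superiority (Step 3) goes untested for dropout bias because the tipping search covers only non-inferiority. Analyses 3b and 3c are prespecified for superiority, use in-trial data and do not rely on MAR. Small tipping penalties for Step 3 also require a borderline result. At an assumed observed difference of -0.16 the penalties are about 0.57 (2%) and 0.29 (4%), but at -0.20 they are about 2.3 and 1.2. At the planned -0.1 the upper limit is about +0.05, so there is no superiority finding to tip.

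The contradiction between stated aim and data remains, as does the absence of any in-trial tipping search.

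**Conclusion.** The point holds as a mismatch between purpose and data. Analyses 5 and 6 yield a tipping value for analysis 4, while the text attributes it to the primary analysis, against the plan's own in-trial rule. The primary MAR assumption is not untested, since 3a applies a 0.4 penalty in-trial; what is missing is the escalating version.

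The consequence is limited. Under the planning inputs the two values are roughly 6.8 and 11.8 percentage points, neither plausible in a population entering at 7.0-9.0%, and the non-inferiority decision is unlikely to change. Those figures assume the same starting estimate in both datasets, equal imputed shares in the two arms, no between-imputation variance, and imputed shares of 4% and 2%. More missing data or a less favourable difference would bring both values down, and it would then matter more which analysis the reported value describes. The correction is worth making because it costs almost nothing and attaches the robustness statement to the right result.

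**What to change.** In SAP 2.3:

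1. Under the sensitivity analyses for the primary estimand, add a tipping-point analysis on the in-trial imputed datasets of analysis 1. Add the penalty to faster aspart subjects whose week-16 HbA1c is imputed there, and raise it until non-inferiority no longer holds. Report that penalty as the robustness value for the primary non-inferiority conclusion.
2. Keep analyses 5 and 6 on on-treatment data, but state their aim as testing analysis 4 (secondary estimand). Analysis 6 need not be repeated in-trial: subjects stopped for non-eligibility are asked to attend the remaining key visits, so few should have an imputed in-trial value to exempt.
3. Record the change in SAP section 3.

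A tipping value for HbA1c superiority, if Step 3 is confirmed, is optional because 3b and 3c already serve that purpose.

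The cost is a few sentences and a rerun of the same penalty search on datasets that analysis 1 already produces. No new data are needed, and neither the sample size nor any confirmatory test changes. The only downside is one more sensitivity figure to report.

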17.4 Secondary endpoints

17.4.1 Confirmatory secondary endpoints

If the effect of CSII treatment with faster-acting insulin aspart can be confirmed in the primary analysis, the trial also aims to confirm the superiority of CSII treatment with faster-acting insulin aspart, for a number of secondary confirmatory endpoints.

The steps used in the hierarchical testing procedure are as follows:

Step 1 (Primary analysis): HbA_{1c} non-inferiority of faster-acting insulin aspart versus $NovoRapid^{@}$

Step 2: 1-hour PPG increment (meal test) superiority of faster-acting insulin aspart versus NovoRapid[®]

Step 3: HbA_{1c} superiority of faster-acting insulin aspart versus NovoRapid[®]

Step 4: 1,5-anhydroglucitol superiority of faster-acting insulin aspart versus NovoRapid[®]

Step 5: time spent in low IG (≤3.9 mmol/L [70 mg/dL]) superiority of faster-acting insulin aspart versus NovoRapid[®]

The primary estimand for the primary endpoint will be repeated for the confirmatory secondary endpoints, change from baseline in 1-hour PPG increment (meal test), change from baseline in 1,5-anhydroglucitol and change from baseline of time spent in low IG (≤3.9 mmol/L [70 mg/dL]) during CGM 16 weeks after randomisation. The analyses related to these estimands are defined below and will be used for the decisions to continue or not, throughout the hierarchical testing procedure. These analyses will be based on the FAS and use the in-trial observation period.

As sensitivity analyses the secondary analysis associated with the secondary estimand for the primary endpoint will also be repeated for the confirmatory secondary endpoints. The analyses will be based on the FAS and using the on-treatment observation period.

Change from baseline in 1-hour PPG increment 16 weeks after randomisation (meal test) (Step 2)

As the second step of the hierarchical testing procedure, change from baseline in 1-hour PPG increment 16 weeks after randomisation will be tested for superiority of faster-acting insulin aspart compared to Novo Rapid[®].

Protocol	Date:	04 February 2016	Novo Nordisk
Trial ID: NN1218-3854	Version:	4.0	

 Trial ID: NN1218-3854
 Version:
 4.0

 UTN: U1111-1118-2480
 Status:
 Final

 EudraCT no.: 2010-024054-11
 Page:
 115 of 149

The 1-hour PPG increment will be analysed based on the laboratory measured values in the meal test.

The 1-hour PPG increment endpoint will be analysed using the FAS and the in-trial observation period based on a multiple imputation technique where the change from baseline in 1-hour PPG increment at week 16 for subjects withdrawn from trial are imputed based on data from completers in the NovoRapid® arm. Multiple copies (100 copies) of the full dataset will be generated by imputing missing values based on estimated parameters as follows:

- An analysis of variance model with strata (two levels based on use of own CGM or not), previous insulin use (three levels: NovoRapid[®], Apidra[®], Humalog[®]), and region as factors and baseline 1-hour PPG increment as covariate is fitted to the change from baseline in 1-hour PPG increment at week 16 for the NovoRapid[®] group only. The estimated parameters, and the variance, from this model are used to impute missing values using stochastic simulation at week 16 for subjects in both treatment groups in order to generate 100 complete datasets.
- For each of the complete data sets, the change from baseline to week 16 is analysed using an analysis of variance model with treatment, strata (two levels based on use of own CGM or not), previous insulin use (three levels: NovoRapid[®], Apidra[®], Humalog[®]), and region as factors, and baseline 1-hour PPG increment as covariate.
- The estimates and standard deviations for the 100 data sets are pooled to one estimate and associated standard deviation using Rubins formula. From this, the pooled estimates and 95% confidence interval for the treatment difference is calculated.

The superiority will be assessed by comparing the upper limit of the 95% CI to 0. If the upper 95% CI is below 0 then superiority will be confirmed.

Change from baseline in HbA_{1c} 16 weeks after randomisation (Step 3)

As the third step in the hierarchical testing, superiority of HbA_{1c} 16 weeks after randomisation with faster-acting insulin aspart compared to NovoRapid[®] is to be confirmed.

The confidence interval from the primary analysis 1) will be used to determine superiority. Superiority will be confirmed if the upper boundary of the two-sided 95% confidence interval of the mean treatment difference (faster-acting insulin aspart minus NovoRapid[®]) is below 0%.

Change from baseline in 1,5-anhydroglucitol 16 weeks after randomisation (Step 4)

Step 4 in the hierarchical testing procedure is to confirm superiority of change from baseline in 1,5-anhydroglucitol 16 weeks after randomisation with faster-acting insulin aspart compared to NovoRapid[®].

Protocol	Date:	04 February 2016	Novo Nordisk
Trial ID: NN1218-3854	Version:	4.0	

 Trial ID: NN1218-3854
 CONFIDENTIAL
 Version: 4.0

 UTN: U1111-1118-2480
 Status: Final

 EudraCT no.: 2010-024054-11
 Page: 116 of 149

The change from baseline in 1,5-anhydroglucitol will be analysed using a model similar to 1), but with baseline 1,5-anhydroglucitol as a covariate.

Superiority will be confirmed if the upper boundary of the two-sided 95% confidence interval of the mean treatment difference (faster-acting insulin aspart minus NovoRapid[®]) is below 0.

Change from baseline of time spent in low IG (≤3.9 mmol/L [70 mg/dL]) during CGM 16 weeks after randomisation (Step 5)

The time spent in low IG is defined for each Subject at each CGM period as the accumulated time in hours spent below or equal to 3.9 mmol/L [70 mg/dL] from the first valid sensor value divided by the actual duration of the profile. To report the endpoint in minutes per 24 hours the ratio is multiplied by 1440.

Step 5 of the hierarchical testing procedure is to confirm superiority of change from baseline of time spent in low IG (≤3.9 mmol/L [70 mg/dL]) during CGM 16 weeks after randomisation with fasteracting insulin aspart compared to NovoRapid[®].

The change from baseline of time spent in low IG (\leq 3.9 mmol/L [70 mg/dL]) will be analysed with a model similar to 1), but with the baseline value of time in hypoglycaemia as covariate.

